## 5 PROCEDURES

**5.1 Study procedures.** Using lay language, provide a complete description of the study procedures, including the sequence, intervention or manipulation (if any), drug dosing information (if any), use of records, time required, and setting/location. If it is available and you think it would be helpful to the IRB: Upload a study flow sheet or table to the **Supporting Documents** SmartForm in **Zipline**.

*For studies comparing standards of care: It is important to accurately identify the research procedures. See UW IRB [POLICY: Risks of Harm from Standard Care](#) and the draft guidance from the federal Office of Human Research Protections, ["Guidance on Disclosing Reasonably Foreseeable Risks in Research Evaluating Standards of Care"](#), October 20, 2014.*

Subjects will be screened over the phone and, if found eligible, will arrange a date/time with the study coordinator for an additional phone call to review the consent form and engage in the consent process. After consenting to participate in the study, subjects will be asked by the coordinator over the phone any medication information, and will then be sent a link to complete a baseline survey online. The baseline survey will include demographic questions and questions about the participant's diagnosis, employment, and pain history.

Following completion of the survey, subjects will be randomized to either usual care or the treatment group (E-TIPS). Study staff will inform subjects of their assignment and, for those assigned to the E-TIPS treatment, arrange a time for their first treatment session. Participants in both groups will complete REDCap assessments at baseline (within one month prior to randomization), six weeks after randomization, ten weeks after randomization, and six months from randomization. The E-TIPS group will also attend eight 45-60-minute teleconference sessions with therapists over the first 8-10 weeks of treatment and complete home activities between each session using the E-TIPS Participant Manual. Each REDCap assessment will take around 20-30 minutes to complete and each therapy session will last around 45 min-60 min. Therapists will also conduct one 10-15-minute "booster session" with participants approximately two weeks after the final treatment session. Therapy will be administered via telephone, therefore subjects will need to have access to a telephone as well as the Internet to complete surveys. Since the private telephone sessions may be recorded, therapists will make an announcement at the beginning of each session letting participants know that their communication will be recorded for purposes of treatment fidelity monitoring. The sessions will teach subjects a variety of cognitive behavioral skills for managing pain that have been used in our past research studies using the TIPS intervention. These including teaching them basic relaxation skills, strategies for pacing activities, managing pain flare ups, and learning how to change their thoughts to better manage their pain and become aware of how their thoughts can influence their emotions and physical state. They will also discuss in the sessions how to integrate these pain management skills into their daily lives, including at work as needed. The home activities will include relaxation exercises as well as "thought record forms (i.e., worksheets)," which are used in most CBT treatments. Participants may discuss the thought records and other home practice activities they complete using the Participant Manual with therapists, and therapists may use this discussion of home practice activities to gauge participant engagement. We request approval to make minor changes to the Participant Manual (e.g. minor word changes and formatting adjustments) without submitting a modification.

After the 6-month assessment, the usual care group will be offered treatment. While in usual care, participants are free to continue or start any treatment they decide. It is not necessary that they refrain from seeking out mental health or other services.

We will randomly select up to 20 participants proportionally to the diagnostic group domain included in the broader sample and interview them about their experience with E-TIPS treatment. As this is qualitative research, the final sample size will be determined by the point we reach thematic saturation, meaning the point when we are no longer learning new information about the topic/question at hand. We will interview participants by audio-only Zoom using an interview guide. Audio-only Zoom has been selected for ease of recording and

obtaining transcripts for analyses. We will ask participants what they found helpful and not helpful about their treatment and about the barriers and facilitators to the treatment. We will then perform a content analysis.

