**Aim 1: Evaluate the efficacy of the telehealth pain self-management intervention, adapted for employees with physical disability, ("E-TIPS"), relative to a waitlist control in reducing pain interference (primary outcome) in adults with chronic pain and physical disability.**

Hypothesis 1.1. Participants randomized to E-TIPS will report greater improvements in pain interference (primary outcome, measured by PROMIS Pain Interference Scale) compared to participants assigned to control at post-treatment (12 weeks post-randomization, primary endpoint).

Hypothesis 1.2. Improvements in pain interference will be maintained at 6 mo. post randomization.

Although the long-term goal is to promote job retention and enhance employment in employees with chronic pain, we chose pain interference as the primary outcome due to its high association with disability and our ability to detect meaningful change within the study timeframe. We will conduct exploratory analyses to determine whether reductions in pain interference are associated with fewer missed days of work and other employment outcomes.

**Aim 2: Examine the effects of E-TIPS compared to control on secondary outcomes relevant to work, including self-efficacy for pain management, pain intensity, fatigue, mood, and days worked at 12 weeks post-treatment and maintenance of effects at 6-month follow up.**

Hypothesis 2.1. Participants randomized to E-TIPS will report greater short-term (post-treatment) improvements in secondary outcomes compared with control.

Hypothesis 2.2. Participants assigned to E-TIPS will retain treatment benefits at 6-months.

Hypothesis 2.3. Within-subject outcome changes during the 12-week intervention period will be greater than during the waitlist time period.

**Aim 3: Evaluate factors, including treatment adherence, treatment satisfaction, and barriers/facilitators of implementation relevant to future dissemination and large-scale**

**implementation of E-TIPS in employed individuals with physical disabilities and chronic pain.** We will collect measures of treatment adherence, satisfaction, and convenience from participants allocated to E-TIPS. We will assess barriers and facilitators to implementation from the participants' perspectives by collecting information about other factors that influence participation.

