**Hypothesis 3.1.** Participants allocated to E-TIPS will demonstrate high treatment adherence (defined as attending > 6/8 sessions) and report being highly satisfied with the treatment (> 8 on 0-10 numeric rating scale).

**1.6 Study design.** Provide a one-sentence description of the general study design and/or type of methodology.

*Your answer will help HSD in assigning applications to reviewers and in managing workload. Examples: a longitudinal observational study; a double-blind, placebo-controlled randomized study; ethnographic interviews; web scraping from a convenience sample of blogs; medical record review; coordinating center for a multi-site study.*

We propose a randomized (1:1), single blind parallel-group trial comparing the TIPS telehealth pain self-management intervention, adapted to address employment issues (E-TIPS), to a waitlist control in adults with physical disabilities and chronic pain who are employed.

**1.7 Intent.** Check all the descriptors that apply to your activity. You must place an "X" in at least one box.

*This question is essential for ensuring that your application is correctly reviewed. Please read each option carefully.*

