Pain self-management interventions are underutilized, both in the general population and in people with physical disabilities. One of the biggest barriers to their use is reliance on face-to-face delivery, in a clinical setting, during business hours, which limits access to people with physical disabilities who are employed. They must take time off to attend multiple treatment sessions, overcome transportation barriers, and contend with the stigma of seeking behavioral healthcare. In addition, an insufficient number of clinicians are trained in behavioral pain interventions for individuals with physical disabilities.

Telehealth has considerable potential for expanding the reach of pain self-management interventions in employed people with physical disabilities. Remote technology can transcend geographical barriers and target larger populations. These approaches also have inherent scalability and are easy to centralize for public health dissemination. Remote delivery can reduce stigma and lower the threshold for treatment initiation, given that it can be used in the privacy of one's home. Telehealth approaches are also less expensive than traditional psychotherapy.

[name] team has conducted a series of RCTs demonstrating the efficacy and acceptability of telehealth interventions in diverse populations; for example, an 8-session, 1:1, telephone intervention resulted in significant reductions in pain, fatigue, and depressive symptoms in more than half of study participants with MS. Benefits were maintained at 6- and 12-months, and treatment adherence and satisfaction were high – 88% of participants completed all 8 sessions and 94% completed at least 4.

[name] recently completed an RCT (N=188) on the efficacy of a telehealth pain self-management intervention (Telephone Intervention for Pain Study, "TIPS"). Participants with MS, SCI, or LL were assigned randomly to either TIPS or a pain education intervention. All participants received 8, 45-minute individual sessions delivered telephonically by postdoctoral psychology fellows or psychologists. Participants allocated to TIPS had a statistically significant decrease in

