average pain intensity from pre- to post-treatment; further reductions in average pain intensity were observed at 6- and 12-month. Furthermore, 36% of those assigned to TIPS had a clinically meaningful reduction in average pain intensity from pre- to post-treatment. Participants rated the treatment as highly helpful and telehealth delivery as convenient; 98.5% reported that they would recommend the treatment to a friend with physical disability. In sum, this study demonstrated: (1) a decrease in pain intensity over the 12- month course of treatment; (2) that therapeutic alliance was not compromised by telehealth delivery; and (3) that participants with disability and pain found the treatment highly beneficial and convenient. Adherence was excellent with 90% completing all 8 sessions and 91% completing all assessments.

**1.9 Supplements.** Check all boxes that apply, to identify Supplements you should complete and upload to the **Supporting Documents** SmartForm in **Zipline**.

*This section is here instead of at the end of the form to reduce the risk of duplicating information in this IRB Protocol form that you will need to provide in these Supplements.*

Check all That Apply	Type of Research	Supplement Name
	Department of Defense The research involves Department of Defense funding, facilities, data, or personnel.	ZIPLINE SUPPLEMENT: Department of Defense
	Department of Energy The research involves Department of Energy funding, facilities, data, or personnel.	ZIPLINE SUPPLEMENT: Department of Energy
	Drug, biologic, botanical, supplement Procedures involve the use of any drug, biologic, botanical or supplement, even if the item is not the focus of your research	ZIPLINE SUPPLEMENT: Drugs
	Emergency exception to informed consent Research that requires this special consent waiver for research involving more than minimal risk	ZIPLINE SUPPLEMENT: Exception from Informed Consent for Emergency Research (EFIC)

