**2.2 Inclusion and exclusion criteria.**

**a. Inclusion criteria.** Describe the specific criteria you will use to decide who will be included in your study from among interested or potential subjects. Define any technical terms in lay language.

(1) 18 years of age or older; (2) self-reported physical disability (including multiple sclerosis, spinal cord injury, traumatic brain injury, and/or amputation/limb loss); (3) chronic pain defined as daily pain of  $\geq 3$  months duration and  $\geq 3$  average pain intensity in the past week on a 0-10 numerical rating scale; (4) experiences pain for more than 45 out of the past 90 days (defined as 50% of the time or greater); (5) reads, speaks and understands English; (6) has access and is able to communicate over the telephone and internet with or without assistive devices; and (7) is employed, working 15-20 hours per week or more, on average, or earning in excess of substantial gainful activity (approximately \$1200/month).

We will enroll individuals with a range of physical disabilities, because there is no evidence that the type of disability affects responsiveness to the proposed treatment; to maximize the generalizability of the results.

**b. Exclusion criteria.** Describe the specific criteria you will use to decide who will be excluded from your study from subjects who meet the inclusion criteria listed above. Define any technical terms in lay language.

(1) Under the age of 18; (2) cannot read, speak, or understand English; (3) no self-reported physical disability; (4) currently unemployed; (5) plans to retire or leave employment within the study period; (6) earning less than approximately \$1200 per month and working fewer than 15-20 hours per week, on average; (7) cannot communicate or complete assessments over the phone or internet; (8) chronic pain defined as daily pain of  $\leq 3$  months duration and  $\leq 3$  average pain intensity in the past week on a 0-10 numerical rating scale; (9) experiences pain for fewer than 45 out of the past 90 days (defined as 50% of the time or less); (10) currently participating in another chronic pain study or cognitive behavioral therapy (CBT) study

We elected to minimize exclusion criteria to maximize generalizability to the population of employed individuals with chronic pain. Participants may continue pharmacological treatments and other treatments for pain.

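### The up-to-20 interviews on barriers are selected without regard to attendance; on the earlier trials' figures, 20 would include about one or two low attenders, with roughly an 8–29% chance of none

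*Protocol*

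**What the plan says.** The selection rule in Protocol section 5.1 is "We will randomly select up to 20 participants proportionally to the diagnostic group domain included in the broader sample and interview them". The number is open below 20: "the final sample size will be determined by the point we reach thematic saturation". On content, the section says: "We will ask participants what they found helpful and not helpful about their treatment and about the barriers and facilitators to the treatment".

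Aim 3 (section 1.5) is the purpose this serves: "We will assess barriers and facilitators to implementation", from the participants' point of view and with later roll-out in mind. Hypothesis 3.1 in the same section sets the attendance standard: "high treatment adherence (defined as attending > 6/8 sessions", so 6 or fewer sessions falls short of it.

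Section 5.3 (Assessments) has therapists record attendance in REDCap. Attendance is therefore available as a selection factor, but section 5.1 does not use it. No other section arranges for people who missed or left treatment to be interviewed.

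Section 1.8b gives attendance in two earlier trials. For the telephone trial in MS: "88% of participants completed all 8 sessions and 94% completed at least 4". For the TIPS trial (N=188): "Adherence was excellent with 90% completing all 8 sessions and 91% completing all assessments".

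**The concern.** People who missed sessions or stopped early have direct experience of the barriers that kept someone from the treatment. If attendance here is as high as in the earlier trials, they will be a small minority, and a simple random draw balanced on diagnosis will pick up very few of them.

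The stopping rule adds to this. Saturation is reached when new interviews add nothing new. In a sample of which roughly nine in ten attended every session, that point can come before anyone who left has been heard, and nothing in the rule prevents it.

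At stake is how far the Aim 3 account of barriers can be carried over to wider delivery. An account drawn almost wholly from full attenders may make the treatment look easier to implement than it is. The primary and secondary outcomes and the adherence and satisfaction hypothesis are not affected.

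**Working it through.** The documents give no expected number of low attenders among the interviewees, so there is no stated figure to reproduce.

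**Inputs**
- Interviews: n = 20 at most, fewer if saturation comes first (Protocol 5.1).
- MS telephone trial (1.8b): fewer than 4 sessions, 100% − 94% = 6%; fewer than 8 sessions, 100% − 88% = 12%.
- TIPS trial (1.8b): fewer than 8 sessions, 100% − 90% = 10%.
- Protocol cut (1.5): low attendance is 6 or fewer of 8. No rate is given. Everyone with fewer than 4 sessions is inside this group, and everyone in it has fewer than 8, so on the MS trial figures the rate lies between 6% and 12%.
- Arm size: 202 participants (SAP, Statistical Analysis) randomized 1:1 (Protocol 1.6), so about 202 / 2 = 101 in E-TIPS.

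**Formulas.** With p the proportion of low attenders, the expected number is n × p and the chance of none is (1 − p)^n. Proportional balancing on diagnosis is taken as unrelated to attendance.

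**At n = 20**
- p = 0.06: expected 20 × 0.06 = 1.2; chance of none 0.94^20 = 0.290; chance of at most one 0.660.
- p = 0.10: expected 2.0; chance of none 0.90^20 = 0.122; chance of at most one 0.392.
- p = 0.12: expected 2.4; chance of none 0.88^20 = 0.078; chance of at most one 0.289.

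At the protocol's own cut, the expected number is therefore 1.2 to 2.4 and the chance of none about 8% to 29%.

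**If interviewing stops earlier**

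| Interviews | Expected low attenders (p = 0.06 to 0.12) | Chance of none (p = 0.12 to 0.06) |
|---|---|---|
| 20 | 1.2 to 2.4 | 8% to 29% |
| 15 | 0.9 to 1.8 | 15% to 39% |
| 12 | 0.7 to 1.4 | 22% to 48% |
| 10 | 0.6 to 1.2 | 28% to 54% |

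**Sensitivity checks**
- Sampling without replacement (hypergeometric), n = 20: from a pool of 100, the chance of none is 25%, 9.5% and 6% for p = 0.06, 0.10 and 0.12. From a pool of 200 (if usual-care participants treated later are included, which is not stated), it runs from 7% to 27%.
- Unequal acceptance: assume low attenders accept at half the rate of others. Their share of those interviewed becomes 0.5p / (0.5p + 1 − p). For p = 0.06 this is 0.03 / 0.97 = 0.031, and the chance of none at 20 is 53%. For p = 0.12 it is 0.06 / 0.94 = 0.064, and the chance is 27%.

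**Low attenders available.** 101 × 0.06 ≈ 6 and 101 × 0.12 ≈ 12. Inviting all of them fits within 20 interviews and leaves 8 to 14 places for adherent participants even if every one accepts.

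**The case against.** The strongest case on the other side is that this is a sampling preference in a supplementary qualitative component. Random selection gives a cross-section and guards against hand-picking. The interviews also cover skill development, later use of the skills and access to treatment (section 5.3), on which people who received the treatment are proper informants. This stands. It supports keeping a random draw among adherent participants, but not leaving attendance out of the selection.

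A second objection is that Aim 3 has other sources. Section 1.5 plans measures of adherence, satisfaction and convenience and other information on participation, and section 4.6 keeps reasons for declining. This stands in part, and it means there is no single endpoint for barriers that the interviews alone decide. However, the satisfaction, home-practice and session-setting data in section 5.3 come largely through therapist contact, to which people who stop attending contribute least. Reasons for declining come from people who never enrolled.

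A third is that fuller sampling detail may exist elsewhere. Section 12.2 mentions a separate study protocol and grant proposal, and section 5.1 an interview guide. That is possible, but section 5.1 states a complete rule and attendance is not in it.

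Some stronger readings are tempting, and the documents do not support them:
- A reader might infer that the sample would often contain no low attender. At 20 interviews the chance is 8–29%. It becomes common only if interviewing stops well short of 20 or low attenders decline more often.
- A reader might infer from section 2.2a ("there is no evidence that the type of disability affects responsiveness to the proposed treatment") that balancing on diagnosis is pointless. That statement concerns response to treatment. Barriers to taking part may still differ by diagnosis, so it remains a sensible balancing factor.
- A reader might infer that full attenders met no barriers that mattered. They can describe barriers that they overcame.
- A reader might ask for a fixed quota of 8–10 low attenders, or for saturation to be judged separately among them. With only about 6–12 in the arm, and section 10.8 noting that some participants become impossible to contact, neither could be relied on.

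**Conclusion.** The point holds as a design weakness that should be corrected. Selection for the interviews ignores attendance, and nothing else in the documents ensures that people who missed or left treatment are heard. At the full 20, about 1.2 to 2.4 low attenders are expected, with roughly an 8–29% chance of none. Even one or two would be too few to describe that group's barriers.

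This rests on three assumptions: that attendance resembles the two earlier trials, that low attenders accept interviews as readily as others, and that the rate at 6 or fewer sessions lies within the 6–12% bracket. This trial's own attendance is not in the documents. Lower attendance here would ease the problem; lower acceptance or an early stop would worsen it.

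**What to change.** In section 5.1, keep the limit of 20 and add attendance as a selection stratum, using the existing cut (more than 6 of 8 sessions versus 6 or fewer):

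- Invite all participants with 6 or fewer sessions.
- Draw the remaining interviewees at random from adherent participants, keeping diagnosis as a balancing factor.
- Do not declare saturation before the low attenders have been approached.
- Report interviewees' attendance, and report themes by attendance group.

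The documents do not say whether the interviews are finished. If they are, report the interviewees' attendance distribution and limit the conclusions on barriers to the kind of participant actually heard.

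The cost is a short addition to the text and use of attendance data already in REDCap. The interview limit and the $25 payment (section 4.4) do not change. The downsides are small: fewer interviews with full attenders, less exact proportionality by diagnosis, and possibly lower acceptance among low attenders.

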## 5.2 MRI scans. Will any subjects have a Magnetic Resonance Imaging (MRI) scan as part of the study procedures?

*This means scans that are performed solely for research purposes or clinical scans that are modified for research purposes (for example, using a gadolinium-based contrast agent when it is not required for clinical reasons).*

	No	→ If no, go to question 5.3 .
	Yes	→ If yes, answer questions a through c.

